**D.4d3. Analytic approaches:** Our non-randomized evaluation design is necessary because randomization was not possible due to our partnership with VISN leadership and outreach efforts for individual site participation. A key goal is to demonstrate to VISN and facility leadership the value of implementation; therefore, we will estimate implementation outcomes for each of our individual sites and pool implementation sites as appropriate. This will allow us to provide descriptive quantitative information about individual implementation efforts to be combined with qualitative findings about implementation success. Although these analyses will allow for some comparison of effectiveness across individual team efforts, we do not propose formal direct comparisons of teams. There are several statistical limitations to the non-randomized evaluation design that we will address through pragmatic approaches. To account for secular trends in increased use of MOUD that may not be due to our implementation efforts, we will track other related implementation efforts such as initiation of additional SCOUTT efforts, and monitor national dashboards to generate a secular rate among non-intervention sites. We will use this secular rate and test to determine if CONDUIT activities increase use of MOUD above this rate, rather than a null hypothesis of 0. Because we are calculating outcomes for each of the individual sites, the risk of a spurious finding due to multiple testing is possible. We will use caution when interpreting any moderate p-values (e.g. 0.01 to 0.05) as significant. For ease in reporting to VISN and site leadership, we will utilize direct pre- and post-implementation period comparisons. Additional multivariate adjusted analysis using time-to-event semi-parametric methods will also be explored. These models will focus on initiation of MOUD treatment, and will allow for examining clinical and demographic characteristics, including time from initial OUD diagnosis.

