**D.5. Specific Aim 3. Estimate the cost of implementation and return on investment**

**D.5a. Overview:** We use well-established methods with which our team has extensive experience to estimate the costs of implementation and return on investment with the primary goal of helping VISN leadership evaluate adoption, scale and spread of the clinical programs we implement.

**D.5b. Economic outcomes:** The primary economic outcome across all projects is cost per additional Veteran initiating MOUD. This includes both implementation costs and costs of delivering the clinical program/intervention. Return on investment will also be calculated and will include total costs including concurrent/downstream treatment and medical care costs.

**D.5c. External facilitation costs:** Cost and expenses associated with EF activities will be directly captured through monitoring of expenses associated with QUERI funding as well as VISN contributions. We anticipate that nearly 100% of support from QUERI will be allocated to implementation activities and tracked across the implementation efforts. Efforts that cannot be allocated individually to a specific clinical program (e.g. general interviews with national stakeholders) will be split equally across the relevant EF teams. Implementation staff will be asked to log collateral hours of effort they incur in excess of the QUERI and VISN support. Each month each investigator and project coordinator on the Implementation Core and each EF team will be asked to confirm that the effort allocated to the project (e.g. 10% FTE) and report how those hours were allocated to mutually exclusive implementation activities such as outreach/coordination with sites, planning, training, technical assistance, feedback, evaluation. This effort will be conducted in coordination with the VISN20 Tele-

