**D.5g. Implementation, clinical and cost outcomes analysis:** We will aggregate the personnel time and financial resource data collected to calculate the total cost of IF for each implementation effort. Using an "intent-to-treat" approach with person-years as the unit of analysis, we will calculate separate multilevel mixed models for each clinical/RE-AIM outcome and cost outcome. We will pool implementation efforts across clinical settings as appropriate (e.g. all primary care implementation efforts will be combined into a single analysis). Exposure to IF implementation-as-usual conditions will be based on timing and randomized as appropriate to each project, such as stepped-wedge designs. We will account for clustering of patients across multiple exposure periods, as well as nesting of patients within clinical settings. This approach will allow assignment of at-risk Veterans to different facilitation levels as well as control for secular trends in pre-post implementation efforts. At-risk Veterans who were initially exposed to implementation-as-usual condition will be censored relative to outcome assessment for that phase if they or their provider is exposed to IF. The model will include an indicator variable for implementation and clinic program status, and an interaction between time and this indicator variable to assess for the independent effect of implementation separate of secular trends. Longer term costs, such as 12-month medical care cost trajectories following exposure to potential referral to MOUD will be included as appropriate. Markov models based on the outcome of the point estimates from the clinical and economic outcome models will be developed to estimate confidence intervals of key measures such as cost per additional at-risk patient receiving MOUD.

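### As worded, the confidence interval for cost per additional Veteran on MOUD is built from point estimates only, and no rule covers an incremental effect near or below zero

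*Combined protocol and SAP*

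**What the plan says.** Section D.5b of the combined protocol and SAP: "The primary economic outcome across all projects is cost per additional Veteran initiating MOUD".

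Section D.5g sets out the modelling in three steps.

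- For estimation, "we will calculate separate multilevel mixed models for each clinical/RE-AIM outcome and cost outcome".
- For dependence, "We will account for clustering of patients across multiple exposure periods", and also for nesting of patients within clinical settings.
- For uncertainty, "Markov models based on the outcome of the point estimates from the clinical and economic outcome models will be developed to estimate confidence intervals". The example it names as a target for these intervals is "key measures such as cost per additional at-risk patient receiving MOUD". This is in substance the D.5b outcome, although D.5b speaks of initiating and D.5g of receiving MOUD.

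Section D.4d3 sets the benchmark for the effect: a secular rate from non-intervention sites, with a "test to determine if CONDUIT activities increase use of MOUD above this rate, rather than a null hypothesis of 0". It adds that "we will estimate implementation outcomes for each of our individual sites and pool implementation sites as appropriate".

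The available text names no standard errors, covariance, input distributions, bootstrap, probabilistic sensitivity analysis, Fieller interval or net-benefit measure for the economic outcome. It gives no instruction for an incremental effect that is zero, negative or indistinguishable from zero.

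**The concern.** A Markov model turns inputs into outputs. If the inputs are fixed numbers, a deterministic run returns one number, and a patient-level simulation returns only Monte Carlo error, which the analyst sets by choosing how many patients to simulate. Neither reflects how well the data estimate the effect or the cost. The clustering handled in the mixed models is lost unless it is carried forward. Because cost and outcomes are fitted in separate models, their covariance is not available unless someone plans for it.

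The measure is also a ratio, with additional Veterans starting MOUD, net of secular trend, in the denominator. As the denominator approaches zero the ratio explodes, and below zero its sign no longer has a clear meaning: a negative value could be read as a saving.

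Section D.5a says the economic work is mainly to help VISN leadership judge adoption, scale and spread. An interval that is too narrow, or a ratio with an unstable denominator, could mislead that judgement.

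**Working it through.** **1. The plan's only figure on precision.** Table 6 (section D.4d4) gives effect sizes detectable with power 0.80. Alpha is not stated; I assume 0.05 two-sided. The one-sample formula d = (z₀.₉₇₅ + z₀.₈₀)/√n = (1.960 + 0.842)/√n gives:

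| n | Computed d | Table 6 |
|---|---|---|
| 50 | 0.396 | 0.40 |
| 75 | 0.323 | 0.32 |
| 200 | 0.198 | 0.20 |
| 750 | 0.102 | 0.10 |

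All four agree after rounding. At its design point, then, the effect lies about 2.80 standard errors from its null. I use that as a stand-in for the precision of the denominator, with no allowance for clustering.

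**2. What fixed inputs give.** Assume 23.7% (the national rate in Table 2) before and 28.7% after (my assumption). The standard error of the difference is √{[p₀(1−p₀) + p₁(1−p₁)]/M}.

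| Source | M per period | Standard error |
|---|---|---|
| Real patients | 200 | 0.044 |
| Simulated patients | 10,000 | 0.0062 |
| Simulated patients | 1,000,000 | 0.0006 |

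The simulated error depends on computing time alone.

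**3. What the ratio's interval should look like.** With cost known exactly and the effect at 2.80 standard errors, the Fieller limits relative to the point ratio are 1/(1 + 1.96/2.80) = 1/1.70 = 0.59 and 1/(1 − 1.96/2.80) = 1/0.30 = 3.33. Adding independent cost error, with assumed coefficients of variation (CV):

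| Cost CV | Fieller 95% interval | Denominator held fixed |
|---|---|---|
| 0 | 0.59 to 3.33 | 1.00 to 1.00 |
| 10% | 0.56 to 3.36 | 0.80 to 1.20 |
| 20% | 0.48 to 3.44 | 0.61 to 1.39 |

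Most of the width comes from the denominator, which is the part that fixed inputs drop.

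**4. How often the denominator fails.** The Fieller set is unbounded whenever the effect is not significant at 0.05. With t = d√n, that probability is Φ(1.96 − t) − Φ(−1.96 − t), and P(estimate ≤ 0) = Φ(−t).

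| n | d | t | P(unbounded) | P(estimate ≤ 0) |
|---|---|---|---|---|
| 200 | 0.2 | 2.83 | 19.3% | 0.2% |
| 200 | 0.1 | 1.41 | 70.7% | 7.9% |
| 50 | 0.1 | 0.71 | 89.1% | 24.0% |

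If the true net effect is zero, half of all estimates fall at or below zero.

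**5. Is a non-positive change realistic?** Table 1 (Phase 1, numbers on treatment) shows VA E. Colorado going from 189 (20%) to 173 (19%). Manchester's count fell from 153 to 139 while its rate rose from 22% to 46%, so the sign of the change depends on whether counts or rates are used. These figures show only that the case can arise. They are not initiations and do not size the problem.

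**The case against.** The strongest reply is that this is loose drafting and not a decision to ignore error. The sentence states confidence intervals as its purpose and follows mixed models that handle clustering and will produce standard errors. A probabilistic Markov model centred on the estimates would fit that intention. This stands: nothing in the plan says sampling error will be left out, and a reader who inferred that the method can never give a valid interval would go too far. It does not remove the gap, because point estimates are the only input named and the separate models supply no cost-effect covariance.

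A reader might also infer from D.4d3 that a cost ratio will be reported for every site, many with negative denominators. The documents do not support that. The sentence saying "we will estimate implementation outcomes for each of our individual sites" concerns implementation outcomes. The economic text points to larger units: all projects in D.5b, implementation efforts pooled by clinical setting in D.5g, and return on investment by project in G.1.

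Finally, it is tempting to size the problem from Table 1. The eight count changes (3, −14, 52, −16, 30, 49, 61, 10) sum to 175, and resampling facilities gives about 18 to 330. At equal cost per facility the ratio would run from 175/330 = 0.53 to 175/18 = 9.7 times its point value. Those multipliers should not be relied on. They use on-treatment counts at eight Phase 1 facilities, and they hinge on Manchester. Without it the total is 189, the interval about 48 to 324, and the upper multiplier 189/48 = 3.9. Netting off each facility's own VISN change gives about −46 to 276, with 8.7% of resamples at or below zero. Here, dropping Manchester raises that share to about 21%. The VISN change is also not the planned secular rate, since it includes the facilities themselves.

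**Conclusion.** The concern holds in a limited form. As worded, D.5g derives the interval for the primary economic outcome from point estimates alone. Followed literally, it yields intervals of zero width or with Monte Carlo error only, which are too narrow. Separately, the available text has no rule for an incremental effect near or below zero.

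The 0.59 to 3.33 range and the roughly 20% chance of an unbounded interval at Table 6's design point are illustrations. They assume a two-sided alpha of 0.05, normal and independent cost and effect estimates, no clustering, and a denominator as precise as Table 6 implies. Pooling many sites would narrow the range (at six standard errors with exact cost it is 0.75 to 1.49). Clustering, or a smaller net effect, would widen it. Appendices and some pages were not available, so the absence of a method is judged on the remaining text. The point should be corrected before analysis; it does not undermine the design.

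**What to change.** **Uncertainty.** In D.5g, replace the reference to point estimates. State that Markov inputs will be drawn from the joint sampling distribution of the cost and initiation models, using the estimates and their cluster-adjusted covariance, and give the number of draws. Because the models are fitted separately, say how the covariance between cost and effect will be obtained, for example by joint estimation. Alternatively, use a cluster bootstrap that resamples health systems with their sites and re-estimates both quantities in each resample. Restrict the bootstrap to pooled analyses with enough health systems: Table 2 lists only one for VISN23, where resampling at that level is impossible.

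**Denominator.** State that where the interval for incremental initiations includes zero, incremental cost and incremental initiations will be reported separately, or as net benefit, and not as a ratio. The available text gives no value per initiation, so net benefit would need to be shown over a stated range of values.

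**Definition.** Use one term, initiating or receiving, in both D.5b and D.5g.

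**Cost.** A few sentences of analysis text and modest extra computing; no new data. The intervals will be wider, and some analyses may report no ratio.

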## **F. Study team and relevant experience**

The CONDUIT leadership team brings together a multidisciplinary team of implementation experts, researchers and clinicians. The expertise and broad

experience of this team will allow CONDUIT to work effectively across the continuum of care at implementation facilities using evidence-based IF to leverage resources and address challenges for individual implementation sites. The EF teams will be led by CONDUIT Principal Investigators supported by the Cores (**Table 7**). All members of the leadership team have been integrally involved in Phase 1 activities and have established partnerships with key collaborators at the VISN and facility levels as described above. Individually, the CONDUIT leadership team has extensive experience supported by focused training in Implementation Facilitation. [name] (corresponding PI) has extensive experience with pragmatic effectiveness and implementation research in both OUD and chronic pain and has led several completed and ongoing multi-site projects.

Local resources at CONDUIT leadership team facilities are well-suited to contribute to the team's ability to succeed and include: QUERI centers in West Haven, Iowa City, Denver, Los Angeles, Seattle and Palo Alto; HSR&D Centers of Innovation at all seven CONDUIT leadership facilities; VISN20 VA Center for Excellence in Substance Addiction Treatment and Education (CESATE); VISN19 Vulnerable Veteran Integrated PACT (VIP) Program at the VA Salt Lake City; VISN22 QUERI Complementary and Integrative Health Evaluation Center; and VISN7 Mental Illness Research, Education and Clinical Center (MIRECC). The CONDUIT leadership team is also ideally positioned to ensure productive collaboration with several related national resources and initiatives:

Stepped Care for Opioid Use Disorder (SCOUTT) Initiative: [name] (mPI) and [name] (Co-I) have leadership roles in the implementation and evaluation of SCOUTT.

## **G. Management plan and timeline**

**G.1. Management plan:** [name] will serve as corresponding PI and will lead the CONDUIT Coordinating Center, responsible for overseeing and ensuring integrated, productive interactions among the Cores and among the Cores and the implementation sites. [name] will lead the Veteran Engagement Core. He will be responsible for coordination of recruitment, orientation and prospective administrative support for this group. He will ensure collaboration and alignment with other ongoing Veteran engagement initiatives. [name] will lead the Implementation Core and has extensive experience working as an implementation scientist and leading implementation work across multiple projects. Drs. [name] and [name] will lead the Quantitative /Economic Core. [name] will be responsible for working with the Implementation Core to identify direct analytic support needs. He will oversee analytic staff who will extract and clean data from CDW and REDCap. [name] will oversee economic activities including calculating the cost of implementation efforts, estimating the potential cost savings of initiation of MOUD, and calculating the return on investment of each project.

In the first six months of the project, there will be at least bi-weekly phone meetings for among the Core leads and [name] to ensure coordination across External Facilitation teams (**Table 7**). After six months, these meetings will transition to monthly meetings unless more frequent meetings are necessary. There will also be regular email and telephone contact. The Implementation and Quantitative/ Economics Core will meet weekly with their respective teams. Our operational partners will serve as our Strategic Advisory Group, including 1 to 2 Veterans from the CONDUIT VEB. They will guide the consortium with respect to VHA priorities. There will be a monthly CONDUIT-wide teleconference for all project personnel. Twice annually, the project-wide meeting will include the Strategic Advisory Group. See the Multiple PI Plan for further details about the organization, responsibilities and plans for integration of implementation efforts across the EF teams .

**G.2. Deliverables:** In Phase 2 of this Partnered Implementation Initiative, CONDUIT will build on Phase 1 deliverables to generate several products that will advance OUD care more broadly in VA.

Implementation toolkit: CONDUIT will integrate and iteratively refine current Phase 1 implementation toolkits to comprehensively address the continuum of OUD care (Specialty Care, Primary Care, Acute Care, Telehealth) and improve access and usability by VA stakeholders. For example, the VISN1 External Facilitation team led by [name] and [name] have created and distributed an implementation toolkit to guide MOUD by telehealth. This 54-page Word document covers multiple key domains including clinical, logistical and legal considerations related to buprenorphine prescribing using VHA telehealth.

Training: In Phase 1, all CONDUIT EF teams provided training to key personnel at implementation sites. Buprenorphine is an important tool for expanding MOUD provision across the continuum of care but is currently restricted to providers who have completed at least 8 hours of training (**Table 1** above). For example, during Phase 1, [name] led 12 buprenorphine waiver trainings in VISN19 and nationally. In Phase 2, integration of these EF teams will provide a platform on which to harmonize and expand training opportunities, and this expanded training is a key CONDUIT deliverable.

Provider consultation or technical assistance support: CONDUIT will also leverage and expand upon existing consultation resources available throughout the VHA Medication for Addiction Treatment in the VA (MAT-VA) Initiative. CONDUIT aims to implement at more than 50 facilities, including small, rural community-based outpatient clinics. Longitudinal support and consultation resources will be a key deliverable to support evidence-based OUD care, especially at these CBOCs.

**G.3. Dissemination:** We will provide quarterly briefings to QUERI and key operational partners during the project period so that any preliminary information on effective strategies can be disseminated promptly. We will disseminate our findings and products to the VA clinical community through established MAT-VA Initiative newsletters, email groups, and cyberseminars. We will also disseminate our findings to the scientific community by publishing our findings in implementation and substance use disorders journals including

publications reporting the quantitative, formative evaluation and cost and budget impact findings. We will also present our finding to VA and non-VA audiences at meetings such as AcademyHealth, VA HSR&D, and Addictions Health Services Research. We expect multiple manuscripts will be published, both at the level of the Consortium as well as more focused publications at the level of the External Facilitation team. Building on team members' involvement in prior and current multi-site projects, we will adhere to an explicit process for coordinating and sharing authorship of peer-reviewed manuscripts and other dissemination efforts (See **Multiple PI plan** for additional details on project governance).

**G.4. Future directions:** In year 3 of CONDUIT, we will compete for additional funding to support national expansion as Phase 3 of this Partnered Implementation Initiative. CONDUIT's robust partnerships with national and VISN leadership as well as its collaboration with concurrent, related VHA initiatives will ensure that CONDUIT is prepared to expand on the successes of Phase 2 to implement the evidence-based, effective practice of MOUD across the VHA continuum of care nationally.

**Table 8.** CONDUIT Gantt Chart
